Document Coversheet

Study Title: Creating Harmony at HOME: A Pilot Study of a Telehealth Based Program for Rural Caregivers' Ability to Adapt Home Environments for Adults With ADRD

Institution/Site:	University of Kentucky
Document (Approval/Update) Date:	Protocol 7/17/23
NCT Number:	NCT05202223
IRB Number	66766
Coversheet created:	10/30/23

NCT05202223: Creating Harmony at HOME: A Pilot Study of a Telehealth Based Program for Rural Caregivers' Ability to Adapt Home Environments for Adults With ADRD

Statistical analysis plan:

Analysis included mean and standard deviation of each endpoint at each visit. A linear mixed model was completed to determine if the mean response varied among the 3 visits (P value listed in the last column). Final analyses used a modified intent to treat (mITT) for a completers analysis which included those participants who completed visit 2.

-Which IRB-

Medical
 OnMedical

-Protocol Process Type-

Exemption

IMPORTANT NOTE: You will not be able to change your selections for "Which IRB" and "Protocol Process Type" after saving this section. If you select the wrong IRB or Protocol Process Type, you may need to create a new application.

See below for guidance on these options, or refer to ORI's "Getting Started" page. Please contact the Office of Research Integrity (ORI) at [contact] with any questions prior to saving your selections.

Which IRB

The Medical IRB reviews research from the Colleges of:

- Dentistry
- Health Sciences
- Medicine
- Nursing
- Pharmacy and Health Sciences
- and Public Health.

The Nonmedical IRB reviews research from the Colleges of:

- Agriculture
- Arts and Sciences
- Business and Economics
- Communication and Information
- Design; Education
- Fine Arts
- Law
- and Social Work

Note: Studies that involve administration of drugs, testing safety or effectiveness of medical devices, or invasive medical procedures must be reviewed by the **Medical IRB** regardless of the college from which the application originates.

Which Protocol Process Type

Under federal regulations, the IRB can process an application to conduct research involving human subjects in one of three ways:

- by exemption certification
- · by expedited review.
- by full review;

The investigator makes the preliminary determination of the type of review for which a study is eligible. Please refer to ORI's "Getting Started" page for more information about which activities are eligible for each type of review.

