- the method used for documenting consent
- if applicable, who is authorized to provide permission or consent on behalf of the subject
- if applicable, specific instruments or techniques to assess and confirm potential subjects' understanding of the information

Note: all individuals authorized to obtain informed consent should be designated as such in the E-IRB "Study Personnel" section of this application.

Special considerations may include:

- Obtaining consent/assent for special populations such as children, prisoners, or people with impaired decisional capacity
 Research Involving Emancipated Individuals
- If you plan to enroll some or all prospective subjects as emancipated, consult with UK legal counsel prior to submitting this application to the IRB. Include research legal counsel's recommendations in the "Additional Information" section as a separate document.
- Research Involving Non-English Speaking Subjects For information on inclusion of non-English speaking subjects, or subjects from a foreign culture, see IRB Application Instructions for Recruiting Non-English Speaking Participants or Participants from a Foreign Culture.
- Research Repositories
 If the purpose of this submission is to establish a research repository describe the informed consent process. For guidance regarding consent issues, process approaches, and sample language see the Sample Repository/Registry/Bank Consent Template.

Informed consent will be sought from two groups: Caregivers and patients with advanced dementia. A caregiver responding to the study ad via phone or email to **screening** will be contacted via email or phone call to schedule a screening visit. Consent will be sent to participant following initial contact and indication of interest in research study prior to screening visit.

Caregiver:

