This study will utilize a one-arm, pre/post design. Forty people living with dementia with behavioral disturbance and their primary care partner will receive the H@H intervention (total n=80), a 6-week telehealth intervention delivered by an occupational therapist during weekly visits. Focus groups before and after the intervention with caregiver informants, interventionists, and study facilitators will allow opportunity to refine the intervention specific to the needs of caregivers in rural Appalachia. Caregivers of community-residing persons living with dementia with complaints of behavioral disturbance will be recruited for this project. The University of Kentucky Alzheimer's Disease Research Center and the Kentucky Neuroscience Institute have established contacts throughout the rural Appalachian region which provides access to our targeted population.

Attachments

Subject Recruitment Methods & Advertising

Describe how the study team will identify and recruit subjects. Please consider the following items and provide additional information as needed so that the IRB can follow each step of the recruitment process.

- How will the study team identify potential participants?
- Who will first contact the potential subjects, and how?
- Will you use advertisements? If so, how will you distribute those?
- · How and where will the research team meet with potential participants?
- If applicable, describe proposed outreach programs for recruiting women, minorities, or disparate populations.
- How you will minimize undue influence in recruitment?
- Attach copies of all recruiting and advertising materials (emails, verbal scripts, flyers, posts, messages, etc.).

For additional information on recruiting and advertising:

- IRB Application Instructions Advertisements
- PI Guide to Identification and Recruitment of Human Subjects for Research

This project, located at the University of Kentucky (UK) will use established cohorts, networks, and patient-groups for recruitment. UK is a leading healthcare center for neurology care in the state of Kentucky. UK also has well-established community partnerships and networks within rural, Appalachia Kentucky.

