Visit 2: Baseline data will be collected at Visit 2 consisting of seven surveys/questionnaires completed during the visit with the study coordinator: the Revised Memory and Behavior Problem Checklist, Adult Sensory Profile, Canadian Occupational Performance Measure, 6-Item Revised Caregiver Appraisal Scale; 6-Item Activities of Daily Living; 8-Item Instrumental Activities of Daily Living, Pearlin Mastery assessment, Stait-Trail Anxiety Scale, and Perceived Stress Scale. . The Situational Assessment Activity and Function Profile will be emailed or mailed to you for completion, as well. A focus group will also be held with selected participants. All intervention materials will be mailed to the patient's home following visit 2. Intervention materials will include items which offer environmental modifications to the home, for example:

Visit 3: The Occupational Therapist will meet with you for Visit 3. This will initiate week 1 in the behavior workbook. During this visit, the therapist will complete the Canadian Occupational Performance Measure, the Home Occupational Environment Assessment, and the Situational Assessment of the Home Environment.

Visit 4-8: At the end of each week, you and the patient you care for will meet with an occupational therapist to complete intervention training, as well as review the behavior journal and adverse events. These visits will last approximately one hour.

Visit 9: At the final week of intervention, you will engage in a two-hour session which will involve of adverse events, and completion of the Revised Memory and Behavior Problem Checklist, CES Depression scale; 6-Item Revised Caregiver Appraisal Scale; 6-Item Activities of Daily Living; 8-Item Instrumental Activities of Daily Living; Canadian Occupational Performance Measure, Stait-Trait Anxiety Scale; Zarit Caregiver Burden Scale, Pearlin Mastery assessment and Perceived Stress Scale surveys/questionnaires. A focus group will also be held with selected participants. The focus group will consist of the first ten participants willing to participate. The focus group will last approximately 60 minutes and will be conducted over zoom. The focus group will provide feedback needed to refine the intervention to specific needs of caregivers in rural Appalachia.

Visit 10: Four weeks following completion of the intervention, you will complete a follow up session consisting of the same visit 9 assessments.

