This study will utilize a one-arm, pre/post design. Consent will be obtained electronically using REDCap survey distribution. Researchers will assess the feasibility of the primary outcome: increased caregiver competence (Pearlin mastery sub-scale on caregiver competence). Forty persons with dementia and their caregivers will be recruited for participation from the University of Kentucky Alzheimer's Disease Center (UK-ADRC), UK Telehealth Neurology Clinic, and Kentucky Neuroscience Institute. A sample of 40 caregivers has 80% power to show that the compliance (protocol adherence) rate is =60% versus the alternative that the compliance rate is <60% at the 0.05 level of significance. This sample size will allow for assessment of feasibility as the primary outcome based on retention of =75% of study participants completing the study, with =60% protocol adherence, estimated from current clinical trials at UK-ADRC and rehabilitation feasibility trials. All data will be collected remotely and stored electronically on REDCap servers approved by the University of Kentucky IRB. Statistical analyses will be completed using R and SAS programming Exploratory analyses will be conducted to gather feasibility data on the potential efficacy of with assistance from D the intervention on secondary outcomes, including behavior, functional performance, and caregiver burden, with change from baseline to the end of the study and 1-month post-intervention follow up using analysis of covariance (ANCOVA) that will include prespecified covariates (i.e., age, gender, education, disease state, comorbidities). Frequencies of demographic variables (sex, age, cognitive status, education, caregiver relationship, caregiver age), behavior change, and adverse events will be compared among participants within the same group and between groups for differences using either Fisher Exact or chi-square tests.

[figure not shown]
Intervention description:

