Perceived Stress Scale: Scale to assess caregiver stress.

6-Item Revised Caregiver Appraisal Scale: Assessment of caregiver satisfaction related to intervention.

Revised Memory and Behavior Problems Checklist: Caregiver report of behavioral concerns presented by the patient.

Situational Assessment- Activity and Function Profile: Caregiver report of situational elements and patient participation of activities completed within the home.

Situational Assessment of the Home Environment: Therapist led review of home environment accessibility and set up for patient use. Stait-Trait Anxiety Scale: Assessment of caregiver-reported feelings of anxiety.

UCLA Loneliness Scale: Assessment of caregiver-reported feelings of loneliness.

Zarit Caregiver Burden Scale: A brief assessment of caregiver burden associated with patient care, to be completed by the caregiver. Will be mailed or emailed to the caregiver.

Focus groups of the first ten participants who are willing to participate will engage in an online Zoom focus group pre intervention and post intervention with goals to culturally adapt the intervention for those living in Appalachia, and to gain feedback regarding their experience with the intervention.

Feasibility as measured by caregiver competence will be assessed as the primary outcome of this study. Primary outcome: Caregiver mastery will be assessed using the 4-item Pearlin mastery sub-scale on caregiver competence (a=.74) at pre- and post-test and one-month post-intervention follow up. Exploratory outcomes will examine impact of the intervention on caregiver burden (4 item Zarit Burden Interview; a=.78), stress (10-item Perceived Stress Scale; a=.84-.86), the 6-item caregiver appraisal sub-scale on caregiver satisfaction a=.67-.76), and change in BPSD (24-item Revised Memory and Behavior Problems Checklist; a=.67-.90) at pre- and post-test. These measures are included in the attachment.

Attachments

Attachments	
Attach Type	File Name
DataCollection	Focus Group 1 Interview Guide_rev.docx
DataCollection	Focus Group 1 Interview Guide_v2 clean.docx
DataCollection	Focus Group 2 Post Interview Guide_rev.docx
DataCollection	Focus Group 2 Post Interview Guide_v2 Clean.docx
DataCollection	HARMONY AT HOME PARTICIPANT MANUAL 1-16-22.pdf
DataCollection	SAAF.pdf
DataCollection	HARMONY AT HOME PARTICIPANT WORKBOOK highlighted 1-19-22.docx
DataCollection	HARMONY AT HOME PARTICIPANT MANUAL 1-16-22.docx
DataCollection	SAAF revised highlighted 1-19-22.docx

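### A single-arm protocol plans between-group Fisher/chi-square tests without identifying any groups, and the SAP gives one overall three-visit test where the protocol planned two changes from baseline.

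*Combined protocol and SAP*

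**What the plan says.** **Design.** The Study Design section describes a single-arm study: "Forty people living with dementia with behavioral disturbance and their primary care partner will receive the H@H intervention (total n=80"). The statistical paragraph under Research Procedures repeats that design.

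**Group comparisons.** The same paragraph says that frequencies of adverse events, demographic variables and behavior change "will be compared among participants within the same group and between groups for differences using either Fisher Exact or chi-square tests". It does not say what the groups are. The Informed Consent Process section does mention two groups, but only for consent: "Informed consent will be sought from two groups: Caregivers and patients with advanced dementia".

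**Change over time.** For the secondary outcomes (behavior, function, caregiver burden), Research Procedures plans an exploratory analysis "with change from baseline to the end of the study and 1-month post-intervention follow up using analysis of covariance (ANCOVA"), with five named covariates. The SAP on the coversheet, written in the past tense, says "Analysis included mean and standard deviation of each endpoint at each visit" and "A linear mixed model was completed to determine if the mean response varied among the 3 visits (P value listed in the last column"). It mentions no ANCOVA, covariates or contrasts.

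**Time points.** Data Collection & Research Materials places mastery at pre-test, post-test and 1 month. It lists the exploratory outcomes (burden, stress, caregiver satisfaction and "change in BPSD (24-item Revised Memory and Behavior Problems Checklist; a=.67-.90) at pre- and post-test") without a 1-month assessment. At Visit 10, four weeks after the intervention, Research Procedures says "you will complete a follow up session consisting of the same visit 9 assessments".

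**The concern.** A between-group test needs two independent sets of people, and the plan names none. An analyst must either drop the test or invent a grouping, and the reader cannot tell which was intended.

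The second matter is what a reader can learn about change. The protocol asks two specific questions: how far had the outcome moved by the end of the intervention, and how far by 1 month? The SAP's P value answers a broader one: do any of the three visit means differ? It does not say which follow-up differs from baseline, and visit SDs do not give the uncertainty of a within-person change. A pilot is used to plan the next study, so the size of each change and its interval matter more than an overall P value. The SAP test is applied to each endpoint, so it appears to cover Pearlin mastery too, which Research Procedures and Data Collection & Research Materials call the primary outcome.

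**Working it through.** **1. Could the groups be caregivers and patients?** Set against the variables listed in Research Procedures:

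| Variable | Defined for both dyad members? |
|---|---|
| Sex, age, education | Could be |
| Adverse events | Could be |
| Cognitive status | Patient, on the natural reading |
| Caregiver relationship, caregiver age | Caregiver only |
| Behavior change | Patient only |

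Where both members have a value, the 80 people form 40 linked pairs (80 / 2 = 40). Fisher and chi-square tests treat them as 80 independent observations. An age comparison would also partly reflect eligibility, which is 21-99 for caregivers and 65-99 for patients. This reading does not rescue the sentence.

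**2. What do visit means and SDs leave out?** I take the SAP's three visits to be baseline, end of intervention and 1 month; the SAP does not name them. For baseline SD s0, follow-up SD s1 and within-person correlation r:

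- SD of change = sqrt(s0² + s1² − 2·r·s0·s1), which is s·sqrt(2(1 − r)) when both SDs equal s.
- 95% half-width = t(0.975, n − 1) × SD of change / sqrt(n).

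The means and SDs give everything except r. The documents give no correlations, so r is an assumed range. I use n = 40 (planned dyads) and n = 30 (the 75% retention target, 0.75 × 40).

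| r | SD of change | Half-width, n=30 (t=2.045) | Half-width, n=40 (t=2.023) |
|---|---|---|---|
| 0.4 | 1.095 s | 0.409 s | 0.350 s |
| 0.6 | 0.894 s | 0.334 s | 0.286 s |
| 0.8 | 0.632 s | 0.236 s | 0.202 s |

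For example, at n = 30 and r = 0.4: 2.045 × 1.095 / 5.477 = 0.409. An assumed mean change of 0.4 SD at n = 30 would have an interval from −0.01 to 0.81 SD at r = 0.4, and from 0.16 to 0.64 SD at r = 0.8. The same published means and SDs fit both.

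**3. If behavior change is a before/after frequency.** The protocol does not say what behavior change is compared with. If it is one category per dyad, such as improved or not, pairing does not arise. If it is a before/after frequency in the same dyads, the planned tests ignore the pairing. Exact enumeration of all paired 2×2 tables, assuming n = 30, 60% at baseline, a fall to 35% and a two-sided 0.05 level, gives:

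| | Binary correlation 0.2-0.5 | Correlation 0 |
|---|---|---|
| Type I error, chi-square | 0.6-2.8% | 4.9% |
| Type I error, Fisher | 0.2-1.3% | 2.6% |
| Power, chi-square | 50% | 50% |
| Power, Fisher | 35-39% | 40% |
| Power, exact McNemar | 46-67% | 39% |
| Power, mid-p McNemar | 55-78% | 47% |

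Under this reading, and with positive correlation, the planned tests are conservative. Exact McNemar is not better everywhere: at correlation 0.2 it has 46% power against 50% for chi-square. That is why the mid-p version is preferred below. Every input here is assumed.

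**4. Time points.** Burden is collected at Visit 1, and stress, satisfaction and behavior problems at Visit 2. All four recur at Visit 9 and, through the repeat rule, at Visit 10. The ANCOVA sentence also plans a 1-month analysis. The list in Data Collection & Research Materials that stops at post-test does not agree with either.

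**The case against.** The strongest reply is that these are drafting matters in a feasibility pilot. Caregivers and patients are both treated as participants and have separate procedure lists, so sex, age and adverse events could be tabulated for each. Attached files that are not part of the public document might define the groups. A mixed model suits three repeated measures in one arm, and within-person change in behavior is analysed by that model whatever the Fisher/chi-square sentence means. Visit means show the direction, size and timing of mean change.

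Most of this stands. Tabulating by role is sensible; testing dyad-linked groups as independent is not. The model is sound, and the visit means do carry the size and timing of mean change. What remains missing is the precision of that change and a statement of which follow-up differs from baseline.

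Three stronger readings are tempting, and the documents support none of them:

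- **The model was changed after the results were seen.** The SAP is retrospective and gives no date or reason. That leaves the timing unknown; it does not show a data-driven switch. Even the replacement of the ANCOVA is inferred from the SAP's silence.
- **The mixed model inflates false positives.** A random-intercept-only model would have 9-11% type I error for baseline to 1 month if visit correlations decay (assumed 0.6, 0.4-0.5 and 0.8), but about 5% if they are equal at 0.5. The SAP does not state its covariance structure, so no error is shown.
- **The two analyses would reach different conclusions.** Any rate of disagreement depends on how the ANCOVA is set up. In a single arm it tests mean change only through the intercept with centred covariates, and the protocol does not say this.

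**Conclusion.** The point holds and is minor. The between-group comparison has no identified groups, and the one available pairing breaks the independence assumption; this rests on the text alone. The SAP omits the two changes from baseline that the protocol planned for the secondary outcomes, and gives no interval for within-person change on any endpoint, apparently including mastery. For equal visit SDs and correlations of 0.4-0.8, the unreported half-width spans 0.24-0.41 SD at n = 30 and 0.20-0.35 SD at n = 40. These figures, and those for paired frequencies, are illustrative, because the documents give no rates or correlations. The paired-test issue applies only under the before/after reading. The time-point mismatch is a plain inconsistency. The choice of a mixed model is not at fault.

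**What to change.** 1. In Research Procedures, delete the between-group comparison, or name independent subgroups and keep Fisher/chi-square for those only. Describe demographics with counts, and adverse events with counts and exact 95% CIs.
2. In the SAP, for each endpoint and alongside the three-visit test, report the mean changes from baseline to end and from baseline to 1 month with 95% CIs, from paired changes or an unstructured visit covariance. State that the mixed model was used instead of the protocol's ANCOVA. Label any contrast not in the protocol as post hoc.
3. State what behavior change means. Only if it is a before/after frequency in the same dyads, replace Fisher/chi-square with a mid-p McNemar test.
4. Reconcile the time points in Data Collection & Research Materials with Visit 10 and the planned 1-month analysis.

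The cost is wording in both parts of the document and a small re-analysis of existing data; no new data are needed. Because the SAP is retrospective, contrasts added now that the protocol did not plan can only be post hoc.

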Delivered via telehealth, Harmony at HOME (H@H) aims to train caregivers of persons with moderate to severe ADRD in the skills of assessing and modifying the home environment to promote "person-environment fit," a concept that posits that the ability to access features within a built environment (e.g. bathroom, stairs,) or that factors within the environment itself (lighting, noise level, temperature), especially when linked with individualized social support, contribute to or even shape behavior. In ideal circumstances, adults adjust or adapt to meet the demands of the environment; likewise, in the ideal, environments are designed in ways that facilitate positive behaviors. ADRD progressively interferes with an individual's capacity to self-optimize person-environment fit; in such cases, caregivers have the opportunity to create a supportive environment that negates some behavioral challenges and encourages functional activity engagement. H@H seeks to help caregivers acquire the skills and sense of mastery that will enable them to create such supportive environments within the homes of people with dementia.

H@H will be tested with caregivers and the person living with dementia in the Appalachian region of rural Kentucky, a region with the poorest healthcare options for older adults in the country and plagued with extremely high rates of co-morbid conditions, including ADRD. Access to quality caregiver training, in-home caregiver support, and respite is significantly limited. This pilot study will enable the investigators not only to establish the feasibility of the program but to demonstrate this capacity with a population of caregivers and persons with dementia that is in particular need and difficult to reach.

Objectives

List your research objectives. Please include a summary of intended research objectives in the box below.

This Stage 1b pilot project aims to establish the feasibility of H@H and to provide a preliminary test for its mechanism of action (instruction, coaching, and performance review) to improve caregiver mastery in decreasing or eliminating BPSD in people living with dementia. It does so by developing and strengthening their caregivers' skills of assessing and modifying the care environment to foster improved person-environment fit for the person living with dementia (patient).

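### The protocol gives two conflicting primary outcomes, the SAP estimates neither feasibility rate, and the adherence power sentence contradicts itself

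*Combined protocol and SAP*

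**What the plan says.** **Primary outcome.** The design and analysis paragraph of Research Procedures states: "Researchers will assess the feasibility of the primary outcome: increased caregiver competence (Pearlin mastery sub-scale on caregiver competence"). A few sentences later it states: "This sample size will allow for assessment of feasibility as the primary outcome based on retention of =75% of study participants completing the study", and adds a 60% protocol adherence criterion. The outcomes paragraph of Data Collection & Research Materials then says "Feasibility as measured by caregiver competence will be assessed as the primary outcome of this study", and goes on to name the Pearlin sub-scale at pre-test, post-test and one month, without mentioning retention or adherence.

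**Aims.** The Objectives section keeps the two ideas apart. The project "aims to establish the feasibility of H@H and to provide a preliminary test for its mechanism of action", and the second numbered objective is feasibility over telehealth. The intervention description also lists feasibility and the promise of caregiver mastery as two things.

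**Sample size.** Research Procedures claims that 40 caregivers give "80% power to show that the compliance (protocol adherence) rate is =60% versus the alternative that the compliance rate is <60" (per cent). The significance level is 0.05. No assumed true rate and no sidedness are stated. The Pearlin score has no power statement.

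**SAP (coversheet).** It consists of three sentences. The first is descriptive: "Analysis included mean and standard deviation of each endpoint at each visit". The second gives the model: "A linear mixed model was completed to determine if the mean response varied among the 3 visits". The third gives the analysis set: "Final analyses used a modified intent to treat (mITT) for a completers analysis which included those participants who completed visit 2". Retention statistics appear elsewhere only as content of the semi-annual monitoring report (Data and Safety Monitoring, 3.3). That list does not include adherence.

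**The concern.** Feasibility is the leading aim of this pilot and the only basis given for n=40. A mastery score cannot measure it: scores among those who stayed say nothing about how many stayed or how many followed the protocol. If feasibility is read as being measured by competence, a favourable change in the Pearlin score could be presented as a feasibility result even if many dyads left. With two outcomes carrying the same label, either could also be presented as the primary one once results are known.

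The SAP does not resolve this, because it plans no proportion for retention or adherence. The power sentence, which should tie the sample size to the feasibility criterion, sets out to show one hypothesis while naming the opposite one as the alternative.

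**Working it through.** **1. Which outcome is primary**

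| Place | Called primary | Retention/adherence mentioned |
|---|---|---|
| Research Procedures, first use | Pearlin competence | No |
| Research Procedures, second use | Feasibility: 75% retention, 60% adherence | Yes |
| Data Collection & Research Materials | Feasibility, defined as competence; then Pearlin | No |

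The first two rows name different quantities. The third equates them, although the Objectives list them separately.

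**2. What the SAP delivers**

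- Pearlin score: measured at three time points, so the means, SDs and mixed model over 3 visits can cover it.
- Retention and adherence: no proportion, no interval, no comparison with 75% or 60%.
- Denominator: those who completed visit 2. Research Procedures numbers the baseline visit as Visit 2, but the SAP may mean the second of its three analysis visits. On the first reading, people who consented and did not complete baseline are left out. On the second, everyone lost before that visit is left out, and retention to that visit would be 100% by construction. Neither reading is an all-enrolled denominator.

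**3. Trying to reproduce the 80%**

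Inputs from Research Procedures: n = 40, level 0.05, boundary 0.60. Missing: true rate and sidedness. Assumption: the printed equals sign before 60% is a lost ≥. The stated figure therefore cannot be recomputed directly. Instead, solve for the true rate p that would give it, using the exact binomial, X ~ Bin(40, p).

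*Printed direction (alternative below 60%), one-sided 0.05.* At p = 0.60, P(X ≤ 18) = 0.039 and P(X ≤ 19) = 0.074, so reject at 18 or fewer. Power is P(X ≤ 18 | p):

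| True p | 0.50 | 0.45 | 0.40 | 0.39 |
|---|---|---|---|---|
| Power | 32% | 57% | 79% | 83% |

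Power is 80% at p = 0.398.

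*Direction of the claim (alternative above 60%), one-sided 0.05.* At p = 0.60, P(X ≥ 30) = 0.035 and P(X ≥ 29) = 0.071, so reject at 30 or more. Power is P(X ≥ 30 | p):

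| True p | 0.70 | 0.75 | 0.79 | 0.80 |
|---|---|---|---|---|
| Power | 31% | 58% | 80% | 84% |

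Power is 80% at p = 0.791.

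*Two-sided 0.05 (0.025 per tail).* Reject at 17 or fewer (P = 0.019), with 80% power at p = 0.373; or at 31 or more (P = 0.016), with 80% power at p = 0.813.

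*Check by normal approximation, one-sided.* Power = Φ[(|p − 0.60|√40 − 1.645√(0.60 × 0.40)) / √(p(1 − p))] is 80% at about p = 0.407 (low side) and p = 0.782 (high side), in line with the exact results.

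None of these true rates appears in the documents. They are a range under assumptions, not the plan's own inputs.

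**4. Precision available instead**

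Assume one yes/no result for each of 40 dyads. Exact (Clopper-Pearson) 95% limits are the 0.025 quantile of Beta(x, n − x + 1) and the 0.975 quantile of Beta(x + 1, n − x).

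- Retention on the criterion: 0.75 × 40 = 30; 30/40 gives 58.8% to 87.3%.
- Adherence on the criterion: 0.60 × 40 = 24; 24/40 gives 43.3% to 75.1%.

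**The case against.** Several points on the other side carry weight.

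- **The power sentence may describe a futility test.** Testing adherence of at least 60% against less than 60%, and declaring the programme infeasible on rejection, is coherent. Only the claim of showing 60% clashes with it. A reader might infer that the hypothesis is provably reversed, or that 80% is wrong. The documents support neither inference: n=40 is compatible with 80% power in either direction, and nothing shows which was meant. What stands is that the sentence is inconsistent and cannot be reproduced.
- **The SAP does cover an outcome labelled primary.** Both times a named instrument is attached to the label, it is the Pearlin sub-scale, and its three time points fit the mixed model. A reader might infer that the SAP ignores the primary outcome altogether. It does not; the gap is confined to the two feasibility rates.
- **The protocol states the criteria, and comparing a proportion with a threshold needs no model.** That is true, and the coversheet text reads as a summary of work already done. But neither protocol nor SAP specifies the estimate, denominator or interval, and reporting retention for safety monitoring is not an analysis against 75%.
- **Definitions may sit in attachments.** A schedule of events, participant manual and Human Subjects form are listed but not shown. It therefore cannot be claimed that adherence and completion are undefined, only that the visible text does not define them. Visit 10 is a natural reading of completion.
- **The unit is open.** The protocol counts caregiver and patient both as participants (80 in all), and 60% adherence could be a share of tasks per person. The counts 30/40 and 24/40 are therefore conditional.

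**Conclusion.** The concern holds as an internal inconsistency plus a missing feasibility analysis; it is not a fault in the choice of design. The visible text names two primary outcomes and then merges them. An analyst who followed the SAP would produce a Pearlin result but no answer to the feasibility objective or to the criterion that justified the sample size.

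The power claim is unsupported as worded but not shown to be false. With an exact one-sided test at n=40, 80% corresponds to a true adherence near 40% in the printed direction, or near 79% for showing more than 60%. This rests on reading the equals sign as ≥ and on the assumed sidedness.

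A reader might also conclude that the sponsor should now declare one outcome primary. The documents do not support that remedy: the SAP reports its analyses in the past tense, so such a choice would be post hoc even if disclosed. The point should be fixed. Because the remedy is wording and two reported proportions, it does not put the design or the mastery analysis in doubt.

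**What to change.** 1. Delete the sentence that defines feasibility by competence. Treat feasibility (retention, adherence) and Pearlin mastery as separate outcomes, report both, and disclose that the documents conflict on which is primary.
2. Add to the SAP retention and adherence among all enrolled, with exact 95% intervals, set against 75% and 60%. State the unit (caregiver/dyad or individual participant), the visit that counts as completion, and how adherence is derived from existing session and journal records, with its cut-off; or point to the attachment that gives these. Use the number actually enrolled if it is not 40.
3. Reword the power sentence so that the claim and the alternative agree, giving the rate assumed at planning and the sidedness. If these were not recorded, replace it with the precision statement (59% to 87% and 43% to 75% under the yes/no, 40-dyad assumption) and do not choose a rate now. Note that it does not cover the Pearlin outcome.
4. Label every change made after data collection or analysis as post hoc.

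**Cost.** Text edits and two proportions, with no extra visits. Retention figures are already compiled for the monitoring reports. Adherence needs one definition (or a pointer to it) and abstraction for up to 40 dyads from the weekly therapist sessions, engagement checks and returned journals.
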